## **13. DEVIATIONS FROM PROTOCOL PLANNED ANALYSIS**

This section will document any deviations from the protocol planned analysis along with any assessments that were performed on study (and reviewed by the study site) but will not be summarized.

The following assessments were performed or collected on study but will not be summarized:

- Physical examination results (excluding waist circumference, weight, height)
- CYP21A2 genotyping
- Pregnancy test
- Urine drug screen
- Urinalysis
- Testicular ultrasound – locally read data
- Glucocorticoid dose diary data

The following list includes all deviations from the protocol planned analysis:

- The Safety Analysis Set definition in the protocol specified that the subject must have postbaseline safety data during the double-blind placebo-controlled period. This part of the definition was removed from the SAP due to the potential issue of having a subject dosed with study drug and then becoming lost to follow-up.

## **14. PERFORMANCE QUALIFICATION OF SAS® PROGRAMS**

The analysis and summary of data from this study will be performed using SAS® 9.4 (or a later release if available). All SAS® programs used in the production of statistical analyses, tables, listings, and figures described in this SAP will undergo performance qualification (verification that the program produces the intended output) in accordance with department standard operating procedures. The performance qualification may include independent programming and/or peer review of the SAS® log files. In addition, tables, figures, listings, and statistical analysis output will be independently reviewed for completeness and accuracy.

## 16. APPENDICES

### 16.1. Implementation of Multiple Imputation for the Primary Endpoint

The primary efficacy endpoint requires the availability of both the glucocorticoid dose at Week 24 as well as androstenedione values used in the assessment of androstenedione control (as defined in Section 6.3.3). For subjects with incomplete or missing data at Week 24 (ie, missing glucocorticoid dose, androstenedione, or both), the following steps will be taken to multiply impute the missing data for use in the interim and final analysis of the primary endpoint.

Subjects with a missing glucocorticoid dose, androstenedione, or both at Week 24 will have their data multiply imputed using the fully conditional specifications (FCS) method. This method will be implemented in SAS® 9.4 PROC MI using a series of conditional models (one for each incomplete variable at Week 24). First, the missing Week 24 post-dose androstenedione values will be imputed using a regression-based multiple imputation model and the model will include baseline androstenedione (post-GC dose), age, and sex (as specified in the eCRF). The subsequent FCS regression model will impute Week 24 glucocorticoid total daily doses (in mg/m^2/day) and the model will include baseline glucocorticoid dose (mg/m^2/day), baseline androstenedione (post-GC dose), Week 24 androstenedione (post-GC dose), and sex (as specified in the eCRF). Note that a minimum of 0 is set for imputed Week 24 post-GC dose androstenedione values and the Week 24 glucocorticoid daily dose (mg/m^2/day) as it is biologically implausible for either of these values to be less than 0. A random-number generator seed value of 1234 will be used. For subjects missing androstenedione at Week 24, androstenedione “control” will be determined based on the imputed Week 24 androstenedione value and the percent change from baseline to Week 24 in glucocorticoid total daily dose will be set to 0 if the imputed androstenedione value does not indicate “control.” The number of imputed datasets created from the steps above is 100.

The above multiple imputation procedure will be conducted in more than one PROC MI step so that subjects with missing data are correctly imputed from subjects with complete data based on the rules defined below:

- For subjects who are on study drug at Week 24 and are missing one or both components of the primary endpoint, their missing Week 24 data will be imputed from subjects within the same treatment group with non-missing data at Week 24 (Week 24 Completers).
- For subjects who are off study drug at Week 24 and are missing one or both components of the primary endpoint, their missing Week 24 data will be imputed from subjects who are classified as Retrieved Dropouts (Section 6.4). If there are an insufficient number of Retrieved Dropouts, the missing endpoint values will be imputed from subjects in the placebo treatment group. For subjects in the placebo treatment group, missing data will be imputed using non-missing data from subjects in the placebo treatment group.

The multiply-imputed datasets generated from the steps above will be set back together prior to the final analysis steps.

After the multiply-imputed datasets have been created, each of the 100 datasets will be analyzed using the ANCOVA model described in Section 9.2.1. The results of these analyses will be combined using PROC MIANALYZE.

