### **3.3. Sample Size Considerations**

The protocol-specified sample size of 165 subjects (110 in the crinecerfont treatment group and 55 in the placebo group) is based on a power calculation for the primary endpoint and considerations for the size of the safety database. Based on a 2-sample t-test, an effect size of 0.75 with a sample size of at least 90 subjects (60 in the crinecerfont treatment group and 30 in the placebo treatment group) will have greater than 90% power to detect a treatment difference at a 0.05 level of significance. With the full sample size of 165 subjects, there is greater than 90% power to detect an effect size as small as 0.55. Sample size and power estimates were obtained from nQuery® Advisor Version 8.

A single planned interim analysis detailed in Section 5.1, with a futility analysis and an unblinded sample size re-estimation, will be performed when approximately the first 76 randomized subjects (approximately 46% of the planned number of enrolled subjects) have had the opportunity to be assessed for the primary endpoint. The unblinded sample size re-estimation may result in an increase of the overall sample size to a maximum of 210 subjects.

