### 9.1. Multiple Comparisons and Multiplicity

The testing procedure described below will be used to control the familywise Type I error rate for the primary and key secondary endpoints (Figure 1). The promising zone method as planned in this study was shown to not inflate the type I error, as described in the simulation report attached to the Adaptation Plan. All significance levels noted below are 2-sided. All other p-values will not be adjusted for multiplicity and should be considered as nominal p-values.

- The primary endpoint will be tested using a significance level of 0.05.
- If the primary endpoint is statistically significant, then the first 2 key secondary endpoints will be tested using an unequal allocation of significance levels. The change from baseline at Week 4 in androstenedione will be tested using a significance level of 0.02. The achievement of a reduction in glucocorticoid daily dose to physiologic levels ( $\leq 11 \text{ mg/m}^2/\text{day}$  hydrocortisone equivalent adjusted for BSA) will be tested using a significance level of 0.03.
- The family of remaining key secondary endpoints will be tested using the Holm procedure (Holm, 1979). The significance level for this family of endpoints will be dependent on whether the first 2 key secondary endpoints are statistically significant (Wiens, 2003). If both are statistically significant, then the significance level for this family of endpoints will be 0.05. If only one is statistically significant, then the significance level for that endpoint will be used for this family of endpoints. If neither is significant, then this family of endpoints will not be tested for statistical significance. However, nominal p-values will be produced.

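### For on-drug subjects, the primary-endpoint imputation leaves out the Week 12–20 data and any observed Week 24 dose; adding them is a cheap improvement with a small effect

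*SAP*

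**What the plan says.** SAP 16.1 sets out two regression steps and names the predictors of each. For Week 24 androstenedione, "the model will include baseline androstenedione (post-GC dose), age, and sex (as specified in the eCRF". For Week 24 glucocorticoid dose the predictors are baseline dose plus "baseline androstenedione (post-GC dose), Week 24 androstenedione (post-GC dose), and sex (as specified in the eCRF". Nothing from Weeks 12, 16 or 20 appears in either list, and the Week 24 dose is not in the androstenedione model.

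For subjects still on study drug, "their missing Week 24 data will be imputed from subjects within the same treatment group with non-missing data at Week 24". SAP 9.3.1 (item 3) says the same. Off-drug crinecerfont subjects are imputed from retrieved dropouts, or from placebo subjects if retrieved dropouts are too few.

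The omitted data exist. Protocol 9.3.2 schedules a hormone panel at every visit except Weeks 8 and 10, and SAP 6.7 derives a dose at each intermediate visit. SAP 9.3.4 uses Week 20 data, but only in supplementary analyses.

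**The concern.** The design makes Week 20 a strong predictor of Week 24. Protocol 9.3.1 aims to hold the Week 12 dose as stable as possible up to Week 24, with changes at Weeks 16 and 20 driven by androgen control. SAP 9.3.4 accepts the Week 20 dose as a stand-in for a missing Week 24 dose.

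Control at Week 24 decides whether a dose reduction counts or is set to zero. SAP 6.7 foresees a Week 24 visit at which hormone samples were missed. The dose is then known, but if no usable androstenedione pair remains, control is drawn without regard to that dose.

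If subjects who are failing dose reduction are more likely to have missing Week 24 data, an imputation blind to their Week 20 status is too favourable to them. The same imputed datasets serve the interim analysis (SAP 16.1) and the alpha-controlled responder endpoint (SAP 9.4.2).

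**Working it through.** **1. The plan's own figures.** SAP 3.3 gives "The protocol-specified sample size of 165 subjects (110 in the crinecerfont treatment group and 55 in the placebo group") and states that "there is greater than 90% power to detect an effect size as small as 0.55". It also says: "Based on a 2-sample t-test, an effect size of 0.75 with a sample size of at least 90 subjects" (60 and 30) "will have greater than 90% power to detect a treatment difference at a 0.05 level of significance". SAP 9.1 adds: "All significance levels noted below are 2-sided". With power ≈ Φ(d·√(n₁n₂/(n₁+n₂)) − 1.96):

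- 110 and 55, d = 0.55: 0.55 × √36.67 = 3.33, so Φ(1.37) = 91.5% (91.2% by noncentral t).
- 60 and 30, d = 0.75: 0.75 × √20 = 3.35, so Φ(1.39) = 91.8% (91.3% by noncentral t).

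Both claims reproduce. They give the arm sizes but no missing rate, and the change proposed here does not alter them.

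**2. Who is affected (on-drug subjects).**

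- Both components missing: control and dose are both drawn from same-arm completers with similar baseline values.
- Only androstenedione missing: the subject's own dose is kept and only control status is drawn.
- Only dose missing: the observed androstenedione decides control and enters the dose model.

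**3. Size of the bias.** Simulation with 110:55 subjects, 300 trials per setting and 10 imputations. Subjects uncontrolled at Week 20 were weighted 20 times more likely to be missing, and androstenedione was imputed on the log scale. All data-generating values are assumptions. The extended model adds Week 20 dose and androstenedione, and the observed Week 24 dose in the androstenedione model. Entries are mean percent change in dose among the missing subjects, then the treatment difference.

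| Missing | Crinecerfont: true / planned / extended | Placebo: true / planned | Difference: full data / planned / extended | Overstated by plan |
|---|---|---|---|---|
| Both, 5% | −13.3 / −25.1 / −13.2 | −2.1 / −7.4 | −16.78 / −17.14 / −16.78 | 0.36 |
| Both, 10% | −14.0 / −25.7 / −13.6 | −3.1 / −7.8 | −16.69 / −17.34 / −16.70 | 0.65 |
| Androstenedione only, 5% | −13.1 / −16.4 / −13.1 | −1.9 / −2.3 | −16.92 / −17.08 / −16.91 | 0.16 |
| Androstenedione only, 10% | −13.6 / −17.2 / −13.7 | −2.1 / −2.6 | −16.63 / −16.95 / −16.64 | 0.32 |

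Crinecerfont completers averaged −26.3 to −27.0, so only the both-missing rows come out close to a completer. Hand check of the second row, ignoring covariate adjustment: 0.10 × (25.7 − 14.0) − 0.10 × (7.8 − 3.1) = 1.17 − 0.47 = 0.70, near the simulated 0.65. The placebo term shows that the two arms partly offset. Against a standard error of about 2.3, 0.65 / 2.3 = 0.28 standard errors. With missingness unrelated to failing, the largest gap was 17.08 − 16.99 = 0.09.

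**4. Dependence on scale.** The SAP mentions no log transformation. On the raw scale, skewness made the planned model draw too many uncontrolled values. Failing crinecerfont subjects missing both components were imputed at −17 to −18, and the overstatement was at most 0.2 points (16.92 − 16.72). The extended model on the raw scale imputed them at about −9, below the truth, and understated the difference by 0.1–0.3 points.

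**5. Precision if missingness is random.** In a separate illustrative simulation of one arm of 110, error around the full-data mean fell from 0.53 to 0.32 and from 0.84 to 0.54 (36–40%). Combined with a standard error of about 2.3:

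- √(2.3² + 0.53²) = 2.36 becomes √(2.3² + 0.32²) = 2.32, a fall of about 2%.
- √(2.3² + 0.84²) = 2.45 becomes √(2.3² + 0.54²) = 2.36, a fall of about 4%.

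This mixes an arm-level error with the standard error of a difference, so it is approximate.

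**6. Why the change must stop at on-drug subjects.** Assume placebo at −12%, an off-drug crinecerfont subject whose Week 20 value of −28% was reached on drug, equal spread at Weeks 20 and 24, and correlation r. A placebo regression on Week 20 imputes −12 − 16r: −20.0, −23.2 and −26.4 at r = 0.5, 0.7 and 0.9. The planned model gives about −12.

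**The case against.** The affected group may be small. Dose is read from medication start and stop dates, with the safety-laboratory or vital-signs date as fallback (SAP 6.7). For subjects who enter open label, the Week 24 window runs from Day 155 to the first open-label dose (SAP Table 4). A missing post-dose androstenedione falls back to the pre-dose pair, and a pre-dose value within the normal limit counts as control (SAP 6.3.3). A subject who does not tolerate reduction returns to the previous dose (Protocol 7), so failure is normally observed rather than missing. All of this stands, and it is why the point is an improvement and not a threat to the result.

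Planned checks also give partial cover. SAP 9.3.4 substitutes Week 20 data when the Week 24 dose is missing and analyses Week 20/24 averages. SAP 9.3.3 adds complete-case and tipping-point analyses. But the substitution is triggered only by a missing dose, and the tipping point (SAP 16.4) shifts only imputed doses, never imputed androstenedione. Complete-case drops the subjects in question. The averages reach them but change the endpoint. None of these alters the datasets used for the primary, interim and responder analyses.

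A reader might infer that every failing on-drug subject is imputed as an average completer and that the drug effect is materially inflated. The documents do not support that. It applies only when both components are missing, the rule is the same in both arms, and nothing in the documents says that missingness follows failure.

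**Conclusion.** The omission is real and worth correcting, but its effect is small. With 5–10% on-drug missingness strongly related to failing, and androstenedione modelled on the log scale, the plan overstates the treatment difference by about 0.2–0.65 points of about 17. With missingness unrelated to failing, the bias is at most about 0.1 and the gain is about 2–4% of total error. On the raw scale that the SAP text implies, the overstatement is smaller still, though only because two errors offset. The missing rates, the missingness mechanism and the data-generating values are all assumptions.

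A reader might also infer that Week 20 data belong in every imputation step, including the placebo-donor step. They do not. Protocol 13.2 and SAP 9.3.1 make placebo the fallback donor for off-drug crinecerfont subjects, and conditioning on Week 20 values reached on drug would carry the benefit forward and undo that conservative choice.

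**What to change.** For on-drug subjects imputed from same-arm Week 24 Completers:

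- Add Week 20 (or last available Week 12–20) glucocorticoid dose and post-dose androstenedione to both models.
- Include the Week 24 dose in the androstenedione model when it is observed.
- Consider imputing androstenedione on the log scale. In the simulation, the added predictors removed the bias only on that scale.

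Leave the models for off-drug crinecerfont subjects, with retrieved-dropout or placebo donors, as planned. Glucocorticoid type, which is in the ANCOVA, is an optional addition and may be omitted at the interim, where 76 subjects at 2:1 leave about 25 placebo donors (76 / 3). Specify the change before unblinding.

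Cost: a few more variables in the imputation procedure, some intermediate values that must themselves be imputed, and a few more parameters at the interim. Sample size, estimand and significance level do not change.

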## 16.2. Implementation of Multiple Imputation for Key Secondary Endpoints of Serum Androstenedione, HOMA-IR, Weight, and Total Fat Mass

For the key secondary endpoints of serum androstenedione, HOMA-IR, weight, and total fat mass that require multiple imputation, the following steps will be taken:

- 1) For subjects on study drug without the endpoint at the timepoint of interest, impute missing data using a regression-based multiple imputation model based on data from subjects with non-missing endpoint data at the timepoint of interest within the same treatment group. The model will include the baseline value for the endpoint and sex.
- 2) For subjects in the crinecerfont treatment group off study drug without the endpoint at the timepoint of interest, impute missing data using a regression-based imputation model based on data from retrieved dropouts. If there are an insufficient amount of Retrieved Dropouts, the endpoint will be imputed from subjects in the placebo treatment group. For subjects in the placebo treatment group, missing data will be imputed using non-missing data from subjects in the placebo treatment group. The model will include the baseline value for the endpoint and sex.

The number of imputed datasets created from the steps above for each endpoint is 100. After the multiply-imputed datasets have been created, each of the datasets will be analyzed using the ANCOVA model described in Section 9.2.1. The results of these analyses will be combined using PROC MIANALYZE.

## 16.3. Hydrocortisone Dose Equivalent Conversion Factors

The following conversion factors will be used for non-hydrocortisone glucocorticoid medications to determine hydrocortisone dose equivalents.

Glucocorticoid	Hydrocortisone dose equivalent conversion
Methylprednisolone	4×
Prednisolone	4×
Prednisone	4×
Dexamethasone	60×

[Auchus and Arlt, 2013](#); [Speiser et al., 2018](#).

## 16.4. Implementation of Tipping Point Analysis for the Primary Endpoint

A tipping point sensitivity analysis will be performed to assess the robustness of the missing data assumptions for the primary endpoint. The following steps will be taken to implement the tipping point analysis:

- 1) For the 100 imputed datasets created (as described in Section 16.1), if a subject was originally missing the Week 24 glucocorticoid daily dose value ( $\text{mg}/\text{m}^2/\text{day}$ ), add *delta* (see rules below) to the imputed Week 24 glucocorticoid daily dose value. Calculate the percent change from baseline to Week 24 in the glucocorticoid daily dose for all subjects:

- If Week 24 glucocorticoid daily dose is non-missing: percent change from baseline = (Week 24 glucocorticoid daily dose value – baseline glucocorticoid daily dose value) / baseline glucocorticoid daily dose value x 100;
- If Week 24 glucocorticoid daily dose is missing and the subject is in either the crinecerfont treatment group or placebo treatment group: percent change from baseline = (Week 24 delta-adjusted imputed glucocorticoid daily dose value – baseline glucocorticoid daily dose value) / baseline glucocorticoid daily dose value x 100.

- 2) If the subject does not have androstenedione control at Week 24 (as defined in the primary endpoint) then the percent change from baseline will be set to 0 prior to the analysis of the delta-adjusted imputed datasets.
- 3) Analyze the percent change from baseline to Week 24 for the glucocorticoid daily dose in each of the 100 imputed datasets using ANCOVA (as specified in 9.2.1) using PROC MIXED. Use PROC MIANALYZE to combine the results and obtain the LS mean statistics (within treatment, and treatment differences).
- 4) If the p-value in the previous step was not significant (i.e.,  $>0.05$ ), then no additional analyses are needed. If the p-value was significant, repeat the previous steps using the next values of *delta*. Continue to do this until significance is lost, or all combinations of deltas (defined for each treatment group) have been analyzed.

The following rules will be used for defining *delta*:

- The initial delta will be = 0 (ie, an analysis of the original, multiply imputed datasets)
- For subjects in the crinecerfont treatment group, the second delta will be = 1. If this is significant, continue to increase delta by 1 until significance is lost.
- For subjects in the placebo treatment group, the second delta will be = -1. Delta will be decreased by 1 until significance is lost.

Note that if the increment or decrement of delta is too large or too small, then the delta may be adjusted in order to make the number of comparisons reasonable. If significance is not lost or is lost slowly, some values of delta may be omitted from the final table. The tipping point will be defined as the combination of delta values that result in loss of significance.

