The primary endpoint of percent change from baseline in glucocorticoid daily dose at Week 24 is based on the glucocorticoid concomitant medications eCRF. The method of collecting concomitant medication data involves entering a start date and stop date for each medication, unless it is ongoing, in which case the “Ongoing?” field is marked as “yes.” This differs from assessments that are collected discretely at visits. Additionally, the androstenedione values collected at the Week 24 visit are a critical component to the assessment of this endpoint as subjects who do not maintain androstenedione control will have their percent change from baseline value in glucocorticoid total daily dose set to 0. For the purposes of determining the glucocorticoid total daily dose from the eCRF at Week 24, the Week 24 visit date at which the androstenedione values were collected (based on the analysis visit mapping described below) will be used to determine the glucocorticoid dose (as of the same date) to be used for the primary endpoint. If a subject has a Week 24 visit performed based on the analysis visit window but androstenedione was not collected at this visit (ie, missed hormone labs), then the analysis visit date from the collection of the safety labs will be used instead for determining the Week 24 glucocorticoid total daily dose. If both hormone and safety labs were missed at the visit, then the vital signs assessment and its respective Week 24 analysis visit date will be used for determining the glucocorticoid total daily dose. The same methodology described above will be used to determine the glucocorticoid total daily dose from the eCRF at each of the other intermediate visits.

[Table 4](#) includes the analysis visit windows for all assessments, with the exception of those assessments that have a broader window due to more infrequent assessments (eg, every 6 months). These more-infrequent assessments include measurements obtained via DXA (bone mineral density and body composition), testicular ultrasound measurements, HbA1c, glucose tolerance test, insulin, bone markers, and lipid panel. These assessments will use the analysis visit windows defined in [Table 6](#), [Table 7](#), and [Table 8](#), as applicable. [Table 5](#) includes the analysis visit windows for subjects who discontinue from study drug prior to OL period or OL/DB period and therefore do not have a first dose date in the OL period or OL/DB period.

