### **9.3.3. Sensitivity Analyses of the Primary Efficacy Results**

The assumptions relative to the ANCOVA model (e.g. linearity, normality) specified for the primary analysis of the primary endpoint will be checked and any violations of these assumptions will be handled through non-parametric statistical methods.

A tipping point sensitivity analysis will be performed to assess the robustness of the missingness assumptions. This sensitivity analysis is based on “delta adjustments” which is a commonly used approach to assess the impact of missing data in clinical trials (O’Kelly and Ratitch, 2014). The imputed Week 24 glucocorticoid daily dose values (from the MI procedure described in Section 16.1) for subjects in either the crinecerfont treatment group or the placebo treatment group will be delta-adjusted (with a range of plausible penalties for each treatment group) until the treatment difference at Week 24 is no longer statistically significant. The implementation procedure for the tipping point analysis is described in Appendix 16.4. The combinations of delta adjustments that tip the result from statistically significant to insignificant along with the corresponding insignificant p-values will be presented in a table and may be presented in a figure.

A complete-case sensitivity analysis will also be performed to test the robustness of the multiple imputation procedure. The ANCOVA analysis for the primary endpoint will be repeated using only subjects with observed data at Week 24. Subjects who are missing the Week 24 primary endpoint will be excluded from the analysis.

Descriptive statistics and LS means for the sensitivity analyses will be presented by treatment group along with the LS-mean treatment difference, 95% confidence intervals, and nominal p-values.

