## 16.6. Implementation of Tipping Point Analysis for the Key Secondary Endpoint: Physiologic Glucocorticoid Daily Dose Responder

This section will discuss the tipping point analysis for physiologic glucocorticoid daily dose responders which is also a key secondary endpoint as described in Section 9.4.2. This key secondary endpoint is defined as the achievement of a reduction in glucocorticoid daily dose to physiologic levels ( $\leq 11 \text{ mg/m}^2/\text{day}$  hydrocortisone equivalent adjusted for BSA) at Week 24, while Week 24 androstenedione is adequately controlled at  $\leq 120\%$  of baseline or  $\leq \text{ULN}$  for age and sex.

A tipping point sensitivity analysis will be performed to assess the robustness of the missing data assumptions for the glucocorticoid daily dose at Week 24. The following steps will be taken to implement the tipping point analysis for this key secondary endpoint:

- 1) For the 100 imputed datasets created (as described in Section 16.1), if a subject was originally missing the Week 24 value (i.e., missing the glucocorticoid daily dose at Week 24), add *delta* (see rules below) to the imputed Week 24 value. Calculate the change from baseline to Week 24 for all subjects as applicable:
  - If the Week 24 endpoint value is non-missing: change from baseline = (Week 24 value – baseline value).
  - If the Week 24 endpoint value is missing and the subject is in either the crinecerfont treatment group or placebo treatment group: change from baseline = (Week 24 delta-adjusted imputed value – baseline value).
- 2) If the subject does not have androstenedione control at Week 24 (as defined in the primary endpoint) then the change from baseline will be set to 0 prior to the analysis of the delta-adjusted imputed datasets.
- 3) Determine if each subject is a responder or a non-responder. Analyze the categorical data at Week 24 for the values in each of the 100 imputed datasets using the Cochran-Mantel-Haenszel (CMH) test. The CMH test will compare treatment groups (crinecerfont 100 mg bid vs. placebo) and will include the stratification factors used in the randomization. Use PROC MIANALYZE to combine the results and obtain the p-value.
- 4) If the p-value in the previous step was not significant (i.e.,  $>0.05$ ), then no additional analyses are needed. If the p-value was significant, repeat the previous steps using the

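### The tipping-point analyses in SAP 16.4 and 16.6 never shift imputed Week 24 androstenedione, so subjects with an observed dose but a missing hormone value are not stressed

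*SAP*

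**What the plan says.** The primary endpoint needs two Week 24 components: the glucocorticoid dose and an androstenedione value that shows control. SAP 9.3.1 and 16.1 foresee that either or both may be missing and impute whichever is absent. Under 16.1 the imputed hormone value then determines control, and a subject imputed as uncontrolled scores 0%. Section 9.4.2 uses the same imputed datasets for the responder endpoint.

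The planned stress test covers one component:

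- Section 9.3.3 promises: "A tipping point sensitivity analysis will be performed to assess the robustness of the missingness assumptions". It then describes a delta on imputed Week 24 doses only.
- Section 16.4 gives the purpose as "to assess the robustness of the missing data assumptions for the primary endpoint", but adds delta only "if a subject was originally missing the Week 24 glucocorticoid daily dose value". Step 2 afterwards sets anyone without control to 0.
- Section 16.6 has the same trigger ("i.e., missing the glucocorticoid daily dose at Week 24") and a narrower stated scope: "robustness of the missing data assumptions for the glucocorticoid daily dose at Week 24".

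Section 6.7 shows how a subject can have a dose but no hormone value. Dose comes from medication start and stop dates. If "androstenedione was not collected at this visit (ie, missed hormone labs), then the analysis visit date from the collection of the safety labs" is used to read off the dose, and the vital-signs date serves if those labs were missed too.

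**The concern.** A tipping-point analysis is informative only if it can move the assumption in question. For a retained subject who missed the hormone sample, that assumption is whether androstenedione was controlled. In 16.1 the hormone model contains baseline androstenedione, age and sex. It does not contain the Week 24 dose, even when that dose is known, so imputed control takes no account of how far the dose was cut. An on-drug crinecerfont subject is also imputed from completers in the same arm. These are reasonable choices for a primary analysis, but they can be favourable to the drug and so deserve a stress test.

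At stake is what the report may say. If the search finds no tipping point, 16.4 as worded would let that stand for the whole primary endpoint, when one of its two imputed components was held fixed throughout.

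**Working it through.** **The plan's own figure.** Protocol 13.4 and SAP 3.3 give more than 90% power for 110 v 55 at effect size 0.55, two-sided 0.05. A two-sample t calculation gives 91.2% (and 91.3% for 60 v 30 at 0.75), so the statement reproduces. The expected test statistic is Z = 0.55 × √(110 × 55 / 165) = 3.33.

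**The 16.4 rule applied to example subjects.** The illustrative values are baseline 18 and Week 24 dose 10 mg/m²/day. The rule is: add delta if the dose was missing; percent change = (dose − 18)/18 × 100; then set to 0 if uncontrolled.

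| Delta | Hormone only missing, imputed controlled | Hormone only missing, imputed uncontrolled | Dose missing, controlled | Dose missing, uncontrolled |
|---|---|---|---|---|
| 0 | −44.4% | 0 | −44.4% | 0 |
| 1 | −44.4% | 0 | −38.9% | 0 |
| 5 | −44.4% | 0 | −16.7% | 0 |
| 10 | −44.4% | 0 | +11.1% | 0 |
| 15 | −44.4% | 0 | +38.9% | 0 |

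The two hormone-only columns never move. Under 16.6 the first stays a responder throughout (dose 10, at or below 11). The dose-missing, controlled subject becomes a non-responder by delta 5 (dose 15). In placebo, where delta is negative, the adverse direction is a larger counted reduction. An imputed-uncontrolled placebo subject cannot get there, because step 2 returns the score to 0 after any delta.

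**Size of the untested bound.** The following inputs are assumptions, not figures from the documents: 5% of each arm lack only androstenedione; a share p of 0.6-0.8 is imputed as controlled; the reduction is 30-40% in crinecerfont and 20-30% in placebo; the SD is 20. The bound makes every imputed crinecerfont value uncontrolled and every imputed placebo value controlled.

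- Crinecerfont: 0.05 × p × reduction. This is 0.9-1.2 points at p = 0.6 and 1.2-1.6 at p = 0.8.
- Placebo: 0.05 × (1 − p) × reduction. This is 0.4-0.6 points at p = 0.6 and 0.2-0.3 at p = 0.8.
- Same p in both arms: 1.3-1.8 at 0.6 and 1.4-1.9 at 0.8, so 1.3-1.9 overall.
- Different p by arm: from 0.9 + 0.2 = 1.1 to 1.6 + 0.6 = 2.2.
- SE = 20 × √(1/110 + 1/55) = 3.3, so 1.1-2.2 points is 0.3-0.7 SE.

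From Z = 3.33, a loss of 0.7 leaves about 2.6, above 1.96.

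**Flips needed to lose significance at 0.55.** Holding the SD fixed, the crinecerfont mean must lose 0.55 − 1.96/√(110 × 55 / 165) = 0.226 SD. If each flipped subject gives up a reduction of 1 SD, that takes 0.226 × 110 ≈ 25 subjects; for reductions of 2 to 0.5 SD it takes 13 to 50. The assumed 5% supplies 5.5 × (0.6 to 0.8), or about 3-4 crinecerfont flips.

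**The case against.** Four stronger readings are tempting, and the documents do not support them.

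- *That no tipping-point analysis in the SAP shifts anything but dose.* Section 16.5 shifts Week 4 androstenedione, HOMA-IR, weight and fat mass. None of these enters Week 24 control, so the gap is confined to 16.4 and 16.6.
- *That imputed control is never examined.* Two supplementary analyses in 9.3.4 (the Week 20/24 average, and the averaged-baseline version) use the observed visit when the other is missing. Another drops the control rule, and the complete-case analysis in 9.3.3 removes these subjects. These replace, relax or exclude; none assumes that control was lost. Only the adverse bound is absent.
- *That subjects missing both components also escape.* In crinecerfont they do not. The dose delta can carry an imputed-controlled value through 0% and beyond, and past 11 mg/m²/day in 16.6; an imputed-uncontrolled value already sits at 0.
- *That androstenedione is the component most often missing.* The documents give no rate. Section 6.3.3 falls back on the pre-dose pair and accepts a pre-dose value within the normal limit as control. Section 6.7 maps unscheduled and repeat samples into a wide Week 24 window. The affected group may be very small.

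It is also fair that 16.6 claims only to address the dose, so it does what it says. Section 16.4 has no such limit. What survives is a narrow but definite gap between its stated scope and its mechanics.

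**Conclusion.** The point holds in limited form. In 16.4 and 16.6, subjects with an observed dose and imputed Week 24 androstenedione are outside the search, as are placebo subjects imputed as uncontrolled. This limits what a robustness statement can cover; it does not show that the primary result is fragile. The shift scales directly with the proportion missing all usable Week 24 androstenedione and is near zero if few do. The 5% rate, the control rates, the reductions and the SD are all assumed. The wording gap is certain, but its practical effect is unknown until the counts are seen.

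**What to change.** Keep the dose delta for imputed doses only, and leave observed doses unchanged. In 16.4 and 16.6 add a second axis that shifts only imputed Week 24 androstenedione, upward in crinecerfont and downward in placebo, and re-derives control at each step. End it at the bound where all imputed crinecerfont values are uncontrolled and all imputed placebo values are controlled. Report the two-way table and, by arm, the number of subjects missing androstenedione only.

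While editing 16.4, align step 2 with 9.3.2. Step 2 sets every uncontrolled subject to 0, whereas 9.3.2 keeps dose increases regardless of control.

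The cost is SAP wording and a modest extension of the existing program, with no new data. The sponsor also accepts that the robustness statement may come out less favourable.
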